In this international, multicenter, double-blind, phase III, placebo-controlled study, 672 participants will be randomly assigned to receive the standard-dose of benznidazole (300 mg daily for 8 weeks) or the short experimental regimens (benznidazole 300 mg daily for the first 2 weeks plus placebo for the last 6 weeks or benznidazole 300 mg daily for the first 4 weeks plus placebo for the last 4 weeks). Efficacy will be assessed considering a non-inferiority design and through the detection of parasite deoxyribonucleic acid (DNA) through molecular biology (Polymerase Chain Reaction - PCR). Meanwhile, safety will be evaluated through a superiority design, with the aim to find the new regimen as effective as the standard one, but superior in terms of safety. An intention-to-treat analysis will be performed, and statistical significance will be set at 0.025 for the non-inferiority outcome (positive PCR) and 0.05 for the superiority outcome.

The study population will be adult participants, 18 years or older, with chronic Chagas disease in its indeterminate or mild cardiac forms, with a positive diagnosis from two serological assays. The trial will be conducted in four sites: two in Bolivia, and two in Colombia. The primary endpoint will be parasitological response determined as sustained negative qualitative PCR at 24 months after treatment. The proportion of participants with positive qualitative PCR will be measured at 1, 4, 6, 8, 12, 18, and 24 months from end of treatment. The frequency of adverse events leading to treatment discontinuation will be compared. An economic evaluation will be conducted assessing the direct and indirect costs, including procedures associated with the management of adverse events.

Key words

Chagas disease, treatment, short regimen, benznidazole.

1. Rationale and background information

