The main objective of the MULTIBENZ clinical trial was to evaluate the efficacy of different BZN regimens at 12 months post-initiation of treatment in patients with CD in the chronic phase. The primary efficacy outcome was defined as the proportion of patients with suppression of sustained parasitic load in peripheral blood measured by polymerase chain reaction (PCR) during the first 12 months of follow-up after randomization.

Patients were randomly assigned to receive BZN 150 mg/day for 60 days, 400 mg/day for 15 days, or the

standard regimen (300mg/day for 60 days). The total number of patients who were estimated to be included in the study was 240, 60 participants per country and 80 per treatment arm.

The preliminary efficacy analysis of the study (not yet published) did not demonstrate statistically significant differences between the therapeutic regimens evaluated in Bolivia, Argentina, and Colombia. However, patients treated for 15 days had 10% of treatment failure compared with 5% of those receiving the standard regimen (although they did not reach statistical significance).

Therefore, taking into account the results of the MULTIBENZ and BENDITA studies, where different therapeutic regimens have been evaluated, we consider that both the options of Benznidazole 300 mg per day for 2 or 4 weeks, are equally valid to be evaluated in a phase III clinical trial compared to the standard dose of Benznidazole of 300 mg per day for 8 weeks.

3. Objectives and Endpoints

Objectives	Endpoints
Primary	

 To compare the efficacy of BZN in two reduced treatment schemes with a fixed oral dose of 300mg/day for 2 weeks or 300mg/day for 4 weeks compared to the standard treatment of 300mg/day for 8 weeks in the treatment of chronic CD, in its indeterminate or mild cardiac forms. 	
 Proportion of participants with sustained negative PCR at 24 months of follow-up after treatment.
Secondary	

 To evaluate the safety profile of a fixed oral dose of 300mg/day for 2 weeks or 300mg/day for 4 weeks compared to the standard treatment of 300mg/day for 8 weeks in the treatment of chronic CD, in its indeterminate or mild cardiac forms. 	
 Incidence of AE leading to treatment discontinuation.

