10.1 Sample Size Determination

A total sample size of 672 subjects (224 per trial arm, and 336 per country) will be necessary to achieve 90% power to detect a non-inferiority margin difference of 15%, assuming that the standard regimen failure rate is 10% and the intervention regimen is 12%, for a one-sided Z test at a significance level of 0.025. This total sample size has been increased in anticipation in 40% to assure a minimum 60% of participants with active infection (positive PCR) and further by 10% to account for potential losses to follow-up, in order to maintain the specified power and inferiority/superiority margins. This means that individuals removed from the study for the reasons mentioned will not be replaced. This sample size will allow the study to also demonstrate a superiority margin of difference of 10% with 80% power regarding the safety of the experimental arm. Considering the percentage of treatment interruption for conventional treatment of 20%, and a reduction of 50% in the experimental arm, power of 90% and $\alpha=0.05$, 197 patients will be needed in each arm.

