10.3 Statistical Analyses

Categorical variables will be presented as frequencies and percentages and continuous variables as median (interquartile range) or mean (standard deviation) according to the data distribution. Normality of distribution will be checked through histograms and the Kolmogorov-Smirnov test.

The chi-squared test or Fisher exact test will be performed to compare the frequencies across categorical variables and the Mann-Whitney test or Student t-test will be used to compare the continuous variables. Intention-to-treat analysis will be performed to evaluate the efficacy and safety that includes all participants randomized to the study groups. The primary analysis will compare proportion of patients with sustained negative PCR at 24 months in their randomly assigned treatment groups (intention-to-treat analysis). Moreover, the proportion of participants with adverse drug events will be also compared. Comparison analyses between groups will be performed using generalized linear models with a log-link

and binomial distribution. Longitudinal differences on quality-of-life scores between groups will be fitted using linear mixed models.

A per protocol analysis will also be performed. Those participants who do not comply with treatment or permanently interrupt or modify the proposed treatment will be excluded from the analysis unless they had a positive PCR prior to that time-point, in which case they will be included in the analysis and considered as a treatment failure.

For PCR analyses, means and bilateral 95% confidence intervals will be presented by group and visit. In addition, time to sustained parasite clearance until 6, 12, 18 and 24 months of follow-up visits will be assessed using Kaplan–Meier survival analysis with log rank test for significance. Repeated measures analysis will also be performed.

Statistical significance will be set at 0.025 for the non-inferiority outcome (positive PCR) and 0.05 for the superiority outcome (percentage of adverse drug reactions and QOL).

The interim analysis for early stopping will be based on superiority and conducted when all participants have reached 12 months of follow up since the end of treatment. An independent data and safety monitoring board (DSMB) will be convened for this study with expertise in CD, clinical trials as well as biostatistics. The purpose of the DSMB is to analyze the preliminary data at 12 months to help in the decision of interrupting any arm.

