A control event rate is expected to be 10% of treatment failure (at least one positive PCR during follow up period) and a 20% of treatment withdrawn due to any AE. Control arm showing posterior probability of superiority of 97.5% or higher will be considered superior. This will be calculated for the experimental intervention versus the control group based on the observed data at the time of interim assessment with a superiority p-value stopping boundary of 0.010.

The decision for interim analysis will be made in a blinded manner (e.g., based on pooled number of events).

All analyses will be performed using Stata 13.0 for Windows.

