10.9 Safety Analysis

Safety analyses will include all participants who have received at least one dose of the study medication. The proportion of participants with SAE, AESI and/or AEs leading to treatment discontinuation will be described per study arm and by System Organ Class (using preferred terms defined by MedDRA 13.1), according to the CTCAE, version 5. The proportion of participants presenting at least one AE will be described. Participants with multiple events with the same preferred terms will be counted once. The maximum severity grade for each preferred term and body system will be summarized. If multiple events with the same preferred terms are recorded for a participant, the event with the maximum grade will be

included in the analysis. In addition, a narrative for each of the SAEs and AESI will be developed detailing all aspects related to the medical event. AEs not leading to treatment discontinuation will also be described per study arm using the same classification as presented above.

Incidence rate and 95% confidence interval will be presented per study arm will be presented for SAE and AEs per category and most frequent AEs. Otherwise only descriptive statistics will be presented.

Safety laboratory parameters (hematology and biochemistry) will also be described individually per study arm, showing the proportion of participants by degree of elevation relative to ULN and to baseline values and clinical significance, and blood levels changes over time. Shift tables will be presented. A listing of participants experiencing lab parameters elevation will be included.

EKG abnormalities will be described per treatment arm as the proportion of participants per type of EKG finding, clinical relevance and changes over time. Participants with altered EKG may have an echocardiogram to evaluate cardiac involvement or cardiac progression of CD.

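### Section 10.3 gives the 0.05 superiority level to adverse drug reactions and QOL, not to the safety endpoint that the protocol defines and sizes (AEs leading to treatment discontinuation)

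*Protocol*

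**What the plan says.** Five places in the protocol bear on the safety claim.

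- **Abstract:** safety is to be evaluated by a superiority design at 0.05. It also says: "The frequency of adverse events leading to treatment discontinuation will be compared".
- **Section 3 (Objectives and Endpoints):** the safety objective has one endpoint, "Incidence of AE leading to treatment discontinuation". Quality of life is listed under the exploratory objectives, and section 10.10 repeats that status.
- **Section 10.1:** the safety sample size is introduced with "Considering the percentage of treatment interruption for conventional treatment of 20%, and a reduction of 50% in the experimental arm", and 197 per arm is given for 90% power at 0.05. The planned arm size is 224.
- **Section 10.3:** the comparison named for safety is that "the proportion of participants with adverse drug events will be also compared". The significance level is "0.05 for the superiority outcome (percentage of adverse drug reactions and QOL"). Later, in the interim-analysis text, the expected control rate is given as "a 20% of treatment withdrawn due to any AE".
- **Section 10.9:** AEs leading to discontinuation are described by arm, together with SAEs and AEs of special interest. Incidence rates with confidence intervals follow for SAEs and AEs, and then: "Otherwise only descriptive statistics will be presented".

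**The concern.** The trial sets out to show that a shorter course is as effective as the standard one and superior on safety. For the second half of that claim, the outcome that is defined and sized differs from the outcome that is given the significance level.

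These outcomes are not interchangeable. Section 2.1 reports skin rash alone in 29-50% of patients on benznidazole, but treatment stopped in 9-29%. Many reactions therefore do not end treatment, and a regimen could change one frequency without changing the other to the same degree. QOL is a different kind of measure again, analysed by linear mixed models.

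If the text stays as it is, the safety conclusion can rest on whichever sentence is followed: the section 3 endpoint, the percentage with adverse drug reactions, or QOL. The sizing in 10.1 supports only the first.

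**Working it through.** **1. The passages side by side**

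| Place | Safety outcome named | Role |
|---|---|---|
| Section 3 | AEs leading to treatment discontinuation | Secondary endpoint |
| Abstract | AEs leading to treatment discontinuation | To be compared |
| 10.1 | Treatment interruption, 20% v 10% | Sizing |
| 10.3, interim text | Treatment withdrawn due to any AE, 20% | Expected control rate |
| 10.3, analysis text | Adverse drug events; adverse drug reactions and QOL | Comparison; 0.05 superiority level |
| 10.9 | AEs leading to discontinuation | Description |

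The first four rows point to treatment stopped because of AEs. Only the analysis text of 10.3 names something else, and that is where the level is assigned.

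**2. What the sizing refers to**

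Inputs: 20% v 10% and alpha 0.05 (10.1), taken as two-sided because the sidedness is not stated. The unpooled formula is

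n = (z_alpha + z_beta)² × [p1(1−p1) + p2(1−p2)] / (p1−p2)².

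The variance sum is 0.16 + 0.09 = 0.25 and the squared difference is 0.01, a ratio of 25.

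- 80% power: (1.960 + 0.842)² × 25 = 196.2, so 197 per arm.
- 90% power: (1.960 + 1.282)² × 25 = 262.7, so 263 per arm.

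The printed 197 is reproduced at 80% power, not at the 90% printed beside it. That is a separate inconsistency in 10.1. Here it confirms that the sizing is a 20% v 10% calculation for stopping treatment.

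**3. Power at the planned 224 per arm**

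Power = Φ( |p1−p2| / √{[p1(1−p1) + p2(1−p2)]/224} − 1.960 ).

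*Discontinuation, 20% v 10% (protocol figures):* SE = √(0.25/224) = 0.0334; 0.10/0.0334 = 2.993; Φ(1.033) = 0.849. The pooled version gives 0.845.

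*Any adverse drug reaction.* The protocol gives neither a control rate nor an effect. The 40-50% control rates below are an assumption. The effect is taken both ways that 10.1 expresses it: as a 10-point difference and as a 50% reduction.

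| Control v experimental | Variance sum | SE | Difference/SE | Power |
|---|---|---|---|---|
| 40% v 30% | 0.45 | 0.0448 | 2.231 | 0.607 |
| 50% v 40% | 0.49 | 0.0468 | 2.138 | 0.571 |
| 40% v 20% | 0.40 | 0.0423 | 4.733 | 0.997 |
| 50% v 25% | 0.4375 | 0.0442 | 5.657 | >0.999 |

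*QOL:* no effect size or variability is given, so no power can be computed.

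**The case against.** The strongest reply is that the intent is plain. The Abstract says discontinuation will be compared, section 3 defines it, and the general provisions of 10.3 (chi-squared or Fisher tests, log-link binomial models for group comparisons) could be applied to it. This stands in part. A reader might infer that the section 3 endpoint has no planned comparison at all, and the Abstract rules that out. What remains is that 10.3 names other outcomes when it assigns the level.

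The last sentence quoted from 10.9 might be read as forbidding a test of discontinuation. It does not single that endpoint out. The same section describes AEs in general in the same terms, so on that reading it would also cancel the adverse-reaction test in 10.3.

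The word interruption in 10.1 might be read as a third outcome that includes temporary pauses, since sections 8.4 and 9.12 use it that way. But the protocol uses the terms loosely. Section 2.1 has treatment discontinued in up to 29% and section 2.2 calls this interruption; section 9.12 uses discontinuation within a rule on temporary stops. Section 10.3 ties the 20% to withdrawal due to AEs, so the sized outcome can be identified.

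A reader might also conclude that the trial is underpowered for its safety test. The documents do not support that: with the assumed adverse-reaction rates, power runs from about 57% to over 99% depending on the effect. Nor should the 10% allowance for loss to follow-up be taken off 224 here. That follow-up runs for 24 months, whereas this outcome is seen within the 8-week course and 10.9 includes everyone who took at least one dose.

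An unseen SAP does not dispose of the point, because the conflict is between sentences of the protocol itself.

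**Conclusion.** The point holds as a conflict of outcomes. Section 10.3 attaches the 0.05 superiority level to adverse drug reactions and QOL, while section 3 and the Abstract name AEs leading to treatment discontinuation and the sizing is for treatment stopped because of AEs. No other section resolves this.

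The sizing scenario gives about 85% power at 224 per arm (normal approximation, two-sided 0.05), for discontinuation only. For adverse drug reactions power is undefined rather than shown to be low, and for QOL there is nothing to compute.

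This should be fixed before unblinding. It concerns a secondary claim, the intended outcome is recognisable from the rest of the protocol, and the primary PCR non-inferiority analysis is not touched.

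**What to change.** - **10.3:** replace the words in brackets after the superiority level with the section 3 endpoint, the proportion of participants with an AE leading to treatment discontinuation. Bring the sentence on comparing adverse drug events into line with it.
- **10.1:** use that same term in place of treatment interruption.
- **10.9:** state that this endpoint is the tested safety comparison and that the other safety summaries are descriptive.
- Report the percentage with adverse drug reactions and QOL as supportive or exploratory estimates with confidence intervals, without a superiority claim.

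The cost is wording in three sections, with no added participants, visits or data. The sponsor gives up adverse drug reactions and QOL as formal superiority outcomes. When 10.1 is edited, the 90% power printed beside 197 per arm should be reconciled as well.

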4.1 Study overview

Double-blind, non-inferior, phase III, randomized, comparative with three-parallel groups, multicenter, international clinical trial. The trial will be conducted in four study sites (two in Bolivia and two in Colombia).

Each participant will be blindly assigned with a treatment number according to the randomization schedule. The trial drug label will only indicate the trial number, trial site and participant treatment numbers (according to local regulations).

Primary efficacy analyses will be performed when all participants complete the 24 months follow-up visit. Sponsor and study sites staff, including principal investigators (PI), will remain blinded to treatment allocation. A preliminary analysis will be conducted at 12 months. According to this analysis, the study may be interrupted if:

- At that time point, the experimental arms (B300/2 or B300/4) show superiority in terms of treatment failure compared to the control arm (B300/8).

An independent data and safety monitoring board (DSMB) will be convened for this study with expertise in CD, clinical trials as well as biostatistics. The purpose of the DSMB is to analyze the preliminary data at 12 months, to help in the decision of interrupting any arm.

The decision for interim analysis will be made in a blinded manner (e.g., based on pooled number of events). The interim monitoring plan will define monitoring bounds to maintain the two-sided type I error rate at the desired 5% (97.5% or higher probability of superiority over the control group).

5. Study Population

Adult patients will be >18 with weight between 50 kg and 95 kg with serological tests confirming the diagnosis of *T. cruzi* infection. The following eligibility criteria are designed to select patients whose inclusion in the protocol is considered appropriate. All relevant medical and non-medical conditions should be considered when deciding whether a patient may be included. The eligibility criteria cannot be waived by any researcher. Any questions about a patient's eligibility should be discussed with Fiocruz's medical coordinator, prior to the inclusion of the patient.

Prospective approval of protocol deviations to recruitment and enrolment criteria, also known as protocol waivers or exemptions, is not permitted.

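### The 12-month interim stopping rule contradicts itself on direction, gives two thresholds for one look, and does not say which participants are scored as early failures

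*Protocol*

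**What the plan says.** The protocol plans one efficacy interim, "conducted when all participants have reached 12 months of follow up since the end of treatment". Four sections describe it.

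- **Section 4.1.** It says "the study may be interrupted if" the following holds: "At that time point, the experimental arms (B300/2 or B300/4) show superiority in terms of treatment failure compared to the control arm (B300/8"). An interim monitoring plan is to set "monitoring bounds to maintain the two-sided type I error rate at the desired 5" per cent, glossed in brackets as "97.5% or higher probability of superiority over the control group".
- **Section 10.3.** "The interim analysis for early stopping will be based on superiority". It then says "Control arm showing posterior probability of superiority of 97.5% or higher will be considered superior". The next sentence says the quantity is calculated for the experimental intervention against control, "with a superiority p-value stopping boundary of 0.010". The same paragraph defines treatment failure as at least one positive PCR during follow-up.
- **Section 10.8.** The stopping rule will be applied without changing the sample size. If the condition for suspension is met, participants count as early treatment failures.
- **Section 14.** The rule appears under futility. The trigger is a significant difference from standard treatment in parasite DNA 12 months after the end of treatment, with no direction and no level. The early-failure sentence is repeated, here without the condition given in 10.8.

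**The concern.** A stopping rule should tell the DSMB which result triggers action, at what level of evidence, and what happens to the data afterwards. Here each of the three has more than one answer in current text.

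- **Direction.** 4.1 points to experimental superiority, 10.3 names the control arm, and 14 says futility.
- **Threshold.** A 97.5% posterior probability and a p-value of 0.010 are not the same boundary.
- **Scoring.** Read literally, the early-failure sentence would overwrite observed negative PCR results in the primary endpoint.

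By the time of the look everyone is 12 months past treatment, so stopping spares no one drug exposure. It can only cut the follow-up that carries the 24-month primary endpoint. If the ambiguity is settled after the DSMB has seen unblinded results, the choice of rule becomes data-dependent.

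**Working it through.** **Inputs.** 224 per arm and failure rates of 10% (standard) and 12% (short) come from section 10.1; the 10% control rate is repeated in 10.3. The 97.5% and 0.010 thresholds come from 10.3, the two-sided 5% from 4.1, and the historical failure rate of about 20% from 10.4. Three assumptions are mine: the planning rates apply at 12 months, the posterior uses flat Beta(1,1) priors (10.3 names none), and p-values come from a pooled two-proportion z test.

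**The plan's own figure.** 1 − 0.05/2 = 0.975, so 97.5% agrees with 4.1's two-sided 5% for one comparison. It does not agree with 0.010, which corresponds to about 99.0% if one-sided (z = 2.326) or 99.5% if two-sided (z = 2.576), against z = 1.960 for 97.5%.

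**Where the thresholds separate.** With c control failures, e short-arm failures and n = 224:

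z = [(e − c)/n] / √[2p̄(1 − p̄)/n], where p̄ = (c + e)/(2n).

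Take c = 22 (9.8%). For e = 36, p̄ = 58/448 = 0.1295 and z = 0.0625/0.0317 = 1.97.

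| Short-arm failures (v 22) | Posterior, favoured arm better | One-sided p | Two-sided p |
|---|---|---|---|
| 35 | 0.967 | 0.033 | 0.065 |
| 36 | 0.975 | 0.024 | 0.049 |
| 39 | 0.990 | 0.0096 | 0.019 |
| 41 | 0.995 | 0.0049 | 0.0098 |
| 11 | 0.976 | 0.023 | 0.047 |
| 9 | 0.992 | 0.0078 | 0.016 |
| 8 | 0.996 | 0.0041 | 0.0081 |

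Control superiority is therefore crossed at 36, 39 or 41 failures, depending on which threshold is meant; 36 sits right at the 97.5% edge. Experimental superiority is crossed at 11, 9 or 8. Counts of 36–38 (36–40 if 0.010 is two-sided) and 10–11 (9–11) meet one stated threshold and not the other.

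**How likely that is.** Exact binomial enumeration, per comparison, with z = 1.960 standing in for the 97.5% posterior:

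| Failure rates | Crosses 97.5% but not one-sided 0.010 (control superior) | Same, 0.010 two-sided |
|---|---|---|
| 10% v 12% | 5.3% | 7.3% |
| 20% v 22% | 4.0% | 5.6% |

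**What direction changes.** At 10% v 12%:

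| Trigger | 97.5% | One-sided 0.010 | Two-sided 0.010 |
|---|---|---|---|
| Control superior | 10.0% | 4.7% | 2.7% |
| Experimental superior | 0.4% | 0.1% | 0.05% |

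**Error with three equal arms.** Two comparisons share one control, so the correlation is 0.5 (bivariate normal). The chance that either short arm crosses is:

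| | 97.5% | One-sided 0.010 | Two-sided 0.010 |
|---|---|---|---|
| One direction | 4.5% | 1.9% | 0.95% |
| Either direction | 9.1% | 3.7% | 1.9% |

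Only the 97.5% threshold applied in both directions exceeds 5% across the two comparisons. Section 4.1 does not say whether its 5% is per comparison.

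**Scoring.** Suppose 22 v 41 failures at a stop.

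- Only PCR-positive participants count: (41 − 22)/224 = +8.5 points.
- The whole stopped arm counts: (224 − 22)/224 = +90.2 points.
- Everyone counts: 0 points.

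The last two are the extremes of a literal reading, not effects I expect.

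**The case against.** A single rule can be pieced together. If superiority in terms of treatment failure in 4.1 means more failures, then 4.1's bullet, the control-superior sentence in 10.3, the futility label in 14 and the term early treatment failures all describe stopping when a short arm fails more often. On threshold, 97.5% might define superiority while 0.010 governs stopping. On scoring, 10.8 makes the sentence conditional, and the definition of failure in 10.3 suggests only PCR-positive participants are meant. Section 4.1 leaves the bounds to an interim monitoring plan that is not shown, and the DSMB's role is described as helping a decision, which fits the permissive wording in 4.1.

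Some of this stands. The direction conflict narrows on that reading, but it does not absorb the bracket in 4.1, which speaks of superiority over the control group. The split of roles between 97.5% and 0.010 is possible but written nowhere. The contrast between a study that may be interrupted and a rule that will be applied is thin evidence, and I give it little weight. The prior, the scope of the 5% and binding status could properly sit in the monitoring plan. That plan cannot cure values and directions that the protocol itself already fixes in conflict.

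I draw no conclusion from how crossings sit against the 15-point margin. At 22 v 41 the 95% interval is 2.1 to 14.9 points, inside it. With 45/224 control failures (20%), crossings start at 63 and the upper limit is already 15.9, outside it.

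**Conclusion.** The concern holds and should be fixed before the look. The direction, the boundary and the scoring each have more than one reading in current text, and the readings lead to different actions. Direction moves the chance of a 97.5% crossing at the planning rates from 10.0% to 0.4%. The choice of threshold changes the decision in a zone with 4.0% to 7.3% probability per comparison. The scoring sentence, taken literally, replaces observed PCR results in the primary endpoint.

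The probabilities rest on 224 evaluable per arm, on the planning rates (or 20% v 22%) applying at 12 months, and on a flat prior. They would shift with fewer evaluable participants or other rates. The contradictions in the text depend on none of these.

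**What to change.** Amend sections 4.1, 10.3, 10.8 and 14 so that they state one rule in identical words, before any unblinded interim data are seen. The choice of rule is the sponsor's; the passages need to agree on it.

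1. Give one direction for each decision.
2. Give one boundary with its sidedness, and the prior if a posterior probability is kept. Make it consistent with the two-sided 5% in 4.1, and say whether that 5% is per comparison or covers both short arms.
3. Say whether the rule binds the DSMB or advises it.
4. Remove the early-failure sentence from 10.8 and 14, or limit it to participants with a positive PCR, so that the primary endpoint uses observed results.
5. State that the blinded pooled event count governs only the decision to hold the look.

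The cost is one amendment with the approvals that section 13 requires (ethics committees, the WHO review board, and regulators where applicable) and matching wording in the DSMB charter. It needs no extra patients or procedures.
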